Appendix IV – Acceptable Birth Control Methods

Schema

#Cycle = 28 days

*Treatment until disease progression, intolerance or a maximum of 36 cycles

Generic name: Olaparib
Brand name(s): Lynparza
Availability: McKesson

PD at any time
Unacceptable adverse
events
Patient refusal
Investigator's decision

→ EM**

** EM= Event Monitoring

1.0 Background

- 1.1 Biliary cancers (BTC) are a group of rare chemo resistant tumors with one of the worst prognosis among gastrointestinal malignancies.¹

Most patients present with advanced disease at the time of diagnosis where the standard treatment for untreated BTC is the combination of platinum based chemotherapy. The response to GP is heterogeneous, with varying duration of response.² Although the majority of patients (>80%) experience disease control with GP, certain patients are resistant to GP therapy and progress rapidly.^{3,4} However a subset of patients are deemed to be platinum sensitive and receive durable and meaningful responses to platinum based chemotherapy. Genomic profiling studies in solid tumor malignancies, including biliary tract cancer have shown that a significant proportion of BTC express loss of function mutations in genes associated with DNA repair.⁵⁻⁷ These constitute up to 20% of BTC patients, with a higher proportion identified in those with extrahepatic cholangiocarcinoma. This is the highest proportion of DNA repair mutations seen in any gastrointestinal cancer. These genes include, but are not limited to: *ATM*, *ATR*, *BRCA1/2*, *RAD51*, *PALB2*, *PTEN*, *FANC*, *NBN*, *EMSY*, *MRE11*, *ARID1A*. Thus, patients whose tumors express loss of function of genes associated with DNA repair, or homologous recombinant repair (**HRR**), potentially may benefit most from agents aimed against DNA repair mechanisms.

- 1.2 Role of PARP in DNA repair

The PARP family of proteins is comprised of 17 members that catalyse poly (ADP-ribose) lation of proteins by promoting the synthesis and transfer of negatively charged ADP-ribose polyes.⁸⁻¹⁰ Although PARP1 is involved in a diverse range of cellular processes, its major role is in DNA repair. PARP1 is the predominant isoform of the PARP family, accounting for up to 80% of PARP activity.¹¹ PARP2, which exhibits a high degree of structural similarity to PARP1, is also able to promote PARP activity, especially in the absence of PARP1.^{12,13} PARP1 & PARP2 are the only members of the PARP family known to be involved in DNA repair.¹⁴⁻¹⁷ Binding to DNA strand interruptions stimulate the catalytic activity of PARP1 and PARP2 leading to poly (ADP-ribose)lation of key DNA repair proteins.¹⁵

- 1.3 Synthetic lethality of PARP inhibition in HRD cancer cells

In order to combat the detrimental effects of DNA damage, mammalian cells have evolved a complex network of interconnected pathways, proteins known as the DNA damage response (DDR). Homologous recombinant repair (HRR) and non-homologous end joining are the two major pathways involved in the repair of double strand breaks in eukaryotic cells.¹⁸⁻²¹ Two DNA repair proteins with a pivotal role in HRR are BRCA1 and BRCA2. Importantly, there is substantial pre-clinical and clinical evidence demonstrating sensitivity of BRCA1 and BRCA2 deficient cancers to PARP1/2 inhibition. In 2005, two landmark pre-clinical studies showed that PARP1/2 inhibitors have profound activity in cancer cells without functional BRCA1 or BRCA2.^{22,23} In subsequent phase I and II trials, PARP1/2 inhibitors were highly active in ovarian, breast and prostate cancers with germline BRCA inactivating mutations.²⁴⁻²⁸ The potency of PARP 1/2 inhibitors in BRCA-deficient cells arises from a synthetic lethality, where the combination of multiple genomic alterations result in cellular death.²⁹ PARP1/2 inhibition suppresses base excision repair and results in the accumulation of single-strand breaks (SSBs). In turn, SSBs result in

replication fork stalling and collapse that result in the formation of double strand breaks during DNA replication.^{30,31} In cells that express homologous recombination deficiency (HRD), these double strand breaks are either repaired by non-homologous end joining pathway or are left unrepaired, leading to genomic instability and apoptotic cell death.³¹ PARP1 also has a direct role in the HRR pathway at replication forks.³² This dual role of PARP1 in DNA repair and the homologous recombination repair pathway has been postulated as an important factor in the profound activity of PARP1/2 inhibitors in HRD cancer cells.³⁰

Olaparib (AZD2281, KU-0059436) is a potent Polyadenosine 5'diphosphoribose [poly (ADP ribose)] polymerization (PARP) inhibitor (PARP-1, -2 and -3) that is being developed as an oral therapy, both as a monotherapy (including maintenance) and for combination with chemotherapy and other anti-cancer agents.³⁴

PARP inhibition is a novel approach to targeting tumors with deficiencies in DNA repair mechanisms. PARP enzymes are essential for repairing DNA single strand breaks (SSBs).^{25,27,33} Inhibiting PARPs leads to the persistence of SSBs, which are then converted to the more serious DNA double strand breaks (DSBs) during the process of DNA replication. During the process of cell division, DSBs can be efficiently repaired in normal cells by homologous recombination repair (HR). Tumors with HR deficiencies (HRD), such as ovarian cancers in patients with BRCA1/2 mutations, cannot accurately repair the DNA damage, which may become lethal to cells as it accumulates. In such tumor types, olaparib may offer a potentially efficacious and less toxic cancer treatment compared with currently available chemotherapy regimens.

Based on this rationale, we propose a single arm phase II study to evaluate the olaparib for the treatment of advanced biliary cancer expressing DNA repair mechanism defects.

1.4 Correlative Research

PARP inhibitors, such as olaparib act through synthetic lethality in cells with defects in homologous recombination (HR) DNA repair caused by molecular aberrations such as BRCA mutations and is approved for treatment in ovarian cancer and recently breast cancer, with promising clinical activity against other HR defective tumors including breast and prostate cancers. Nonetheless, in the majority of patients, resistance to PARP inhibition inevitably develops, leading to treatment failure. Additionally, a proportion of patients exhibit primary resistance to these drugs despite harboring genomic features of DNA repair deficiency.

Cancer genomes have mutational signatures associated with a variety of pathogenic processes including exposure to exogenous or endogenous mutagens, abnormal DNA editing, the incomplete fidelity of DNA polymerases and failure of DNA repair mechanisms. The latter include mutations and genomic scars associated with loss of wild type BRCA genes and an acquired homologous recombination deficiency (HRD). Clinical studies have shown extensive responses to agents that either increase the level of DNA damage (cisplatin) or interfere with repair of lesions (PARP inhibitors) in patients with pathogenic BRCA germ line variants. Significantly a wide variety of tumors including cancers of the gastrointestinal tract, have a HRD mutational signature even in the absence of pathogenic BRCA variants. The goal of this correlative study will be to determine the mutational profiles of biliary tract cancer in patients enrolled in the phase II study of olaparib. Of significant interest will be the identification of mutations in genes that mediate

DNA repair and HRD related mutational signatures that may correlate with clinical response.

To achieve our goal we will process diagnostic samples from each of 36 patients in the trial using our established flow cytometry and genomic methods. Briefly each sample will be screened by DNA content based flow cytometry to identify tumor and non-tumor populations in biopsies of interest. Once identified each population will be sorted and collected for downstream DNA processing and sequencing.

Cancer biopsies typically have variable levels of stromal and normal cell contamination. However in each case we will prepare tumor and patient matched normal DNA from flow sorted biopsies. Our use of purified flow sorted samples will provide high definition germ line and somatic mutational profiles including the discrimination of heterozygous and homozygous alleles for genes of interest. These will provide a unique data set to explore the associations of mutations and mutational signatures with clinical responses in advanced biliary tract cancer.

2.0 Goals

2.1 Primary

- 2.11 To determine the efficacy (Progression Free Survival (PFS) rate at 1st scan) of olaparib monotherapy in advanced biliary tract cancer (BTC) with mutations in DNA repair genes.

2.2 Secondary

- 2.21 To determine the overall survival of patients with advanced biliary tract cancer with mutations in DNA repair genes treated with olaparib.
- 2.22 To determine the progression free survival of patients with advanced biliary tract cancer with mutations in DNA repair genes treated with olaparib
- 2.23 To determine the objective response of patients with advanced biliary tract cancer with mutations in DNA repair genes treated with olaparib.
- 2.2 To assess the duration of response for patients with advanced biliary tract cancer with mutations in DNA repair genes treated with olaparib who experience an objective response.
- 2.25 To assess the frequency and severity of adverse events in advanced biliary tract cancer patients treated with olaparib.

2.3 Correlative Research

- 2.31 Determine the prevalence of mutations including those targeting DNA repair pathways.
- 2.32 Identify mutational signatures associated with pathogenic process in advanced biliary tract cancer samples

- 2.33 Correlate the presence of mutations and mutational signatures linked to mutations in DNA repair genes and homologous recombinant repair with clinical responses to olaparib
- 2.34 To evaluate putative biomarkers related to: (a) *de novo* sensitivity and (b) tumor evolution and resistance, to PARP inhibition from olaparib in BTC.

3.0 Patient Eligibility

NOTE: Waivers to eligibility criteria are not allowed per ACCRU policy

3.1 Inclusion Criteria

- 3.11 Age ≥ 18 years.
- 3.12 Histological or cytological documentation of metastatic adenocarcinoma of the biliary tract.
- 3.13 Patients with previously identified genetic aberrations that are associated with homologous recombinant repair pathway will be eligible [e.g. somatic mutations in *ATM*, *ATR*, *CHEK2*, *BRCA 1/2*, *RAD51*, *BRIP1*, *PALB2*, *PTEN*, *FANC*, *NBN*, *EMSY*, *MRE11*, *ARID1A*] or germline mutations in the above genes. CLIA-certified assays including commercial tests (Foundation Medicine, Caris, Tempus) will be allowed.
- 3.14 Measurable disease as defined in Section 11.0.
- 3.15 ECOG Performance Status (PS) 0 to 2. (Form is available on the ACCRU web site).
- 3.16 Life expectancy of ≥ 16 weeks per estimation of investigator.
- 3.17 The following laboratory values obtained ≤ 7 days prior to registration.
 - Absolute neutrophil count (ANC) $\geq 1500/\text{mm}^3$
 - Platelet count $\geq 75,000/\text{mm}^3$
 - Hemoglobin ≥ 9.0 g/dL with no blood transfusion in the past 28 days
 - Total bilirubin $\leq 1.5 \times$ upper limit of normal (ULN)
 - Alanine aminotransferase (ALT) and aspartate amino-transferase (AST) $\leq 2.5 \times$ ULN ($\leq 5 \times$ ULN for subjects with liver involvement of their cancer)
 - Serum creatinine $\leq 1.5 \times$ ULN
 - INR/aPTT $\leq 1.5 \times$ ULN

Exception: Patients who are therapeutically treated with anticoagulant agents will be allowed to participate provided that no prior evidence of underlying abnormality in coagulation parameters exists. Close monitoring of at least weekly evaluations will be performed until INR/PTT is stable based on a measurement that is pre-dose as defined by the local standard of care.

 - Alkaline phosphatase limit $\leq 2.5 \times$ ULN ($\leq 5 \times$ ULN for patients with liver involvement of their cancer)
 - Creatinine clearance estimated of ≥ 1 mL/min using the Cockcroft-Gault equation.

Cockcroft-Gault Equation:

Creatinine clearance for males =
$$\frac{(140 - \text{age})(\text{weight in kg})}{(72)(\text{serum creatinine in mg/dL})}$$

Creatinine clearance for females =
$$\frac{(140 - \text{age})(\text{weight in kg})(0.85)}{(72)(\text{serum creatinine in mg/dL})}$$

- 3.18 Negative serum pregnancy test done ≤ 28 days prior to registration and confirmed prior to treatment on day 1, for women of childbearing potential, postmenopausal women or women of childbearing potential with evidence of non-childbearing status.

Postmenopausal is defined as:

- Amenorrheic for 1 year or more following cessation of exogenous hormonal treatments
- Luteinizing hormone (LH) and Follicle stimulating hormone (FSH) levels in the post-menopausal range for women under 50
- Radiation-induced oophorectomy with last menses > 1 year ago
- Chemotherapy-induced menopause with > 1 year interval since last menses
- Surgical sterilization (bilateral oophorectomy or hysterectomy)

- 3.19a Provide informed written consent.
- 3.19b Willing to return to enrolling institution for follow-up (during the Active Monitoring Phase of the study).
- 3.19c Willing to provide blood and tissue for correlative purposes (see Sections 6.0 and 17.0).
- 3.19d HBsAg, anti-HBc and anti-HBs
- 3.19e Patients with chronic HBV receiving any systemic anticancer therapy should receive antiviral prophylactic therapy through and for minimum 12 months following anticancer therapy
- 3.19f Patients with past HBV undergoing other systemic anticancer therapies not clearly associated with a high risk of HBV reactivation should be monitored with HBsAg and alanine aminotransferase during cancer treatment (suggest every other cycle).

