- 3.29g Renal failure requiring hemo-or peritoneal dialysis.
- 3.29h Dehydration CTCAE v5.0 grade ≥2.
- 3.29i Substance abuse, medical, psychological or social conditions that may interfere with the patient's participation in the study or evaluation of the study results.
- 3.29j Known hypersensitivity to any of the study drugs, study drug classes, or excipients in the formulation.
- 3.29k Interstitial lung disease with ongoing signs and symptoms at the time of informed consent.
- 3.29l Persistent proteinuria of CTCAE v5.0 Grade 3 or higher (≥ 3.5 g/24 hrs).
- 3.29m Unable to swallow orally administered medications.
- 3.29n Any malabsorption condition and/or patients with gastrointestinal disorders likely to interfere with absorption of the study medication
- 3.29o Unresolved toxicity greater than CTCAE v5.0 Grade 2 attributed to any prior therapy/procedure excluding alopecia and oxaliplatin induced neurotoxicity ≤Grade 2.
- 3.29p Albumin levels <2.5 g/dl.
- 3.29q Any of the following because this study involves an investigational agent whose genotoxic, mutagenic and teratogenic effects on the developing fetus and newborn are unknown.
 - Pregnant women
 - Nursing women
 - Men or women of childbearing potential who are unwilling to employ adequate contraception

NOTE: Women of childbearing potential and their partners, who are sexually active, must agree to the use of TWO highly effective forms of contraception in combination (as described in Appendix V). This should be started from the time of registration and continue throughout the period of taking study treatment and for at least 1 month after last dose of study drug(s), or they must totally/truly abstain from any form of sexual intercourse (as described in Appendix V).

Male patients must use a condom during treatment and for 3 months after the last dose of olaparib when having sexual intercourse with a pregnant woman or with a woman of childbearing potential. Female partners of male patients should also

use a highly effective form of contraception (as described in Appendix V) if they are of childbearing potential. Male patients should not donate sperm throughout the period of taking olaparib and for 3 months following the last dose of olaparib.

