7.0 Protocol Treatment

7.1 Treatment Schedule - Use actual weight or estimated dry weight if fluid retention

Agent	Dose	Route	Frequency	ReRx
Olaparib	300mg (Starting dose)	PO	Twice Daily (28 day cycle)	Every 28 days

The planned dose of 300 mg taken twice a day will be made up of two (2) x 150 mg tablets, with 100 mg tablets used to manage dose reductions. The planned dose should be taken at the same times in the morning and evening of each day, approximately 12 hours apart with approximately 240 mL of water. The olaparib tablets should be swallowed whole and not chewed, crushed, dissolved or divided. Olaparib tablets can be taken with or without food.

If vomiting occurs shortly after the olaparib tablets are swallowed, the dose should only be replaced if all of the intact tablets can be seen and counted. Should any patient enrolled on the study miss a scheduled dose for whatever reason (e.g. as a result of forgetting to take the tablets or vomiting), the patient will be allowed to take the scheduled dose up to a maximum of 2 hours after that scheduled dose time. If greater than 2 hours after the scheduled dose time, the missed dose is not to be taken and the patient should take their allotted dose at the next scheduled time.

7.2 Patients can be instructed in administration techniques and granted treatment independence with nursing staff approval.

7.3 For this protocol, the patient must return to the consenting ACCRU institution for evaluation at least every 28 days +/- 7 days during treatment.

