If new or worsening pulmonary symptoms (e.g. dyspnea) or radiological abnormality occurs, an interruption in study treatment dosing is recommended and a diagnostic workup (including a high resolution CT scan) should be performed, to exclude pneumonitis. Following investigation, if no evidence of abnormality is observed on CT imaging and symptoms resolve, then study treatment can be restarted, if deemed appropriate by the investigator. If significant pulmonary abnormalities are identified, these need to be discussed with the Principal Investigator.

Renal impairment

If subsequent to study entry and while still on study therapy, a patient's estimated CrCl falls below the threshold for study inclusion (≥ 51 ml/min), retesting should be performed promptly.

A dose reduction is recommended for patients who develop moderate renal impairment (calculated creatinine clearance by Cockcroft-Gault equation or based on a 24 hour urine test of between 31 and 50 ml/min) for any reason during the course of the study: the dose of olaparib should be reduced to 200 mg twice daily.

Because the CrCl determination is only an estimate of renal function, in instances where the CrCl falls to between 31 and 50 mL/min, the investigator should use his or her discretion in determining whether a dose change or discontinuation of therapy is warranted.

Olaparib has not been studied in patients with severe renal impairment (creatinine clearance ≤ 30 ml/min) or end-stage renal disease; if patients develop severe impairment or end stage disease it is recommended that olaparib be discontinued.

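### The steroid rule in the 3.29c NOTE runs opposite to 9.5 and shuts out patients long stable on steroids (minor); the creatinine clearance limit in 3.17 needs a source check against 8.2

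*Combined protocol and SAP*

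**What the plan says.** **Steroids.** Exclusion 3.29c (Section 3.2) deals with symptomatic brain or meningeal tumours and with spinal cord compression. Its NOTE permits a constant corticosteroid dose before and during the study, provided it began 28 days or less before registration. The restricted-medication table in 9.5, in the row on other anti-cancer agents, permits steroids that control symptoms of brain metastases. There the dose must be constant and the start must lie four weeks or more before the first study dose. Section 6.25 puts the first dose between 0 and 7 days after registration.

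**How strictly entry rules apply.** Section 3.0 states: "Waivers to eligibility criteria are not allowed per ACCRU policy". Eligibility is verified at registration (6.22). Section 13.1 makes a patient who misses any entry criterion ineligible, and 16.21 counts only eligible patients as evaluable for the primary endpoint.

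**Creatinine clearance.** In the text extracted from the PDF, 3.17 reads "Creatinine clearance estimated of ≥ 1 mL/min using the Cockcroft-Gault equation". The renal impairment text in 8.2 speaks of a patient whose "estimated CrCl falls below the threshold for study inclusion (≥ 51 ml/min"). The other renal entry limits are serum creatinine at or below 1.5 x ULN (3.17) and "Renal failure requiring hemo-or peritoneal dialysis" (3.29g).

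**The concern.** The two steroid rules bound the same quantity, time since the steroid was started, from opposite sides. The NOTE in 3.29c sets a maximum and 9.5 sets a minimum. A rule meant to secure a steady dose should set a minimum, so 3.29c appears to carry the wrong sign. It also works against its own aim, because it prefers recent starters to patients on a long-established dose.

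Because waivers are barred, a site cannot simply apply the sensible reading. A long-stable patient is turned away or, if treated, counts as ineligible and drops out of the evaluable set. A recent starter is admitted and then stands in breach of 9.5 from the first dose.

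The renal query is separate. Sections 3.17 and 8.2 give different numbers for what should be one entry limit, and a limit of 1 mL/min would screen out nobody.

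**Working it through.** The plan gives no figure of its own on either matter, so there is none to reproduce.

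**Steroids.** Let S be the days from steroid start to registration, and T the days from registration to first dose. Four weeks is taken as 28 days.

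- 3.29c NOTE: S ≤ 28
- 9.5: S + T ≥ 28
- 6.25: 0 ≤ T ≤ 7
- Together: 28 − T ≤ S ≤ 28

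| T (days) | S that meets both rules |
|---|---|
| 0 | 28 only |
| 1 | 27 to 28 |
| 3 | 25 to 28 |
| 7 | 21 to 28 |

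Two cases outside the window:

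- S = 60: fails 3.29c (60 > 28); meets 9.5, since S + T is at least 60.
- S = 10: meets 3.29c; S + T is at most 10 + 7 = 17, so it fails 9.5.

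In general, every S above 28 fails 3.29c while meeting 9.5, and every S below 21 meets 3.29c while failing 9.5. If 3.29c instead required S + T ≥ 28, the two rules would coincide.

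**Creatinine clearance.** The only question here is whether the other entry limits would enforce 51 mL/min if 3.17 really printed 1. The ULN is not in the documents. I assume 0.9 to 1.1 mg/dL for women and 1.0 to 1.3 mg/dL for men, so the creatinine cap (1.5 x ULN) is 1.35 to 1.65 and 1.50 to 1.95 mg/dL. Ages and weights are illustrative. The Cockcroft-Gault formula is the one in 3.17.

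- Woman, 70 y, 60 kg: 70 x 60 x 0.85 = 3570. At the cap, 3570/(72 x 1.35) = 36.7 and 3570/(72 x 1.65) = 30.1 mL/min. Clearance falls below 51 once creatinine exceeds 3570/(72 x 51) = 0.97 mg/dL.
- Man, 70 y, 70 kg: 70 x 70 = 4900. At the cap, 4900/(72 x 1.50) = 45.4 and 4900/(72 x 1.95) = 34.9 mL/min.
- Man, 50 y, 80 kg: 90 x 80 = 7200. At the cap, 7200/(72 x 1.50) = 66.7 and 7200/(72 x 1.95) = 51.3 mL/min.

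So the creatinine cap does not enforce 51 in older or lighter patients, though it does in some others. The dialysis exclusion acts only on patients already on dialysis. A clearance of 1 mL/min in the first patient would need a creatinine of 3570/72 = 49.6 mg/dL, so 1 cannot have been an intended limit.

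**The case against.** **On steroids.** The rules are not strictly incompatible: starts 21 to 28 days before registration can satisfy both. That stands, and a reader who inferred that no steroid-treated patient could comply would go too far. Section 9.5 names only steroids for brain metastases, while the NOTE also sits under meningeal disease and cord compression, so the direct clash is limited to brain metastases. Criterion 3.29c itself admits symptomatic brain disease only more than six months after definitive therapy, with negative imaging, so few such patients will enrol. The sign may also have been misread from the PDF. This is less likely to explain away the conflict, since 9.5 states its rule in words, but the sign should be checked.

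**On creatinine clearance.** The strongest objection is that 1 is exactly 51 with one character lost. Section 8.2 states 51 outright as the inclusion threshold, and its action bands (31 to 50, and 30 or below) lie directly beneath it. A similar loss may show in Section 2.2, where an item numbered 2.2 stands between 2.23 and 2.25, although that could equally be in the source. The objection stands: the documents as available cannot establish an error in 3.17.

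A reader might still infer that the plan lets patients with severe renal impairment start at "300mg (Starting dose") twice daily, in a range of which 8.2 says "Olaparib has not been studied in patients with severe renal impairment (creatinine clearance ≤ 30 ml/min"). The documents do not support that. It depends on an unverified digit. The 8.2 bands are also written for impairment arising on study ("A dose reduction is recommended for patients who develop moderate renal impairment"), and for 31 to 50 mL/min it adds that "the investigator should use his or her discretion in determining whether a dose change or discontinuation of therapy is warranted", so applying them at entry is an inference. Creatinine is measured within 7 days before registration, on Cycle 1 Day 1 and before each cycle (4.0), and 3.29r allows exclusion on judgement. These checks set no numeric clearance limit, but they reduce the risk.

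**Conclusion.** The steroid NOTE in 3.29c is wrong as written, and the point is minor. Subject to the source check on the sign, it sets a maximum where 9.5 sets a minimum. That leaves a common window of at most eight calendar days (days 21 to 28 before registration) and as little as one. The result rests on reading four weeks as 28 days and on the 0 to 7 day interval in 6.25. The number of patients affected cannot be estimated from the documents, but it should be small.

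The creatinine clearance mismatch is a query for the source, not an established defect. If the source does print 1, a correction is warranted, because no other numeric criterion enforces 51; that conclusion uses an assumed ULN and illustrative patients.

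A reader might infer that either matter undermines the primary analysis. Neither does: the Simon boundaries, error rates and sample size do not depend on them. The only link is whether an individual treated patient counts as eligible, and 16.22 already plans 6 extra patients, partly for ineligibility.

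**What to change.** 1. Check the sign in the 3.29c NOTE against the source. If it reads as extracted, change the NOTE to a steady dose begun at least 28 days before the start of study treatment, to match 9.5. Anchoring the 28 days to registration would also satisfy 9.5, since treatment never precedes registration, but it would needlessly exclude some starts on days 21 to 27 that 9.5 can allow.
2. Check the creatinine clearance limit in 3.17 against the source. If it prints 51, do nothing. Only if it prints 1, correct it to 51 mL/min or more (Cockcroft-Gault) and use the same number in the registration check (6.22).

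The cost is one line for the steroid rule and, conditionally, one line plus the registration check for the renal limit, with the usual amendment and IRB review. No procedure is added, because age, weight and creatinine are already needed for the formula in 3.17. If 51 was always intended, no intended patient is lost.
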